9.6.6 Immunogenicity Assessments

The frequency and percentage of subjects with pre-existing antidrug antibody (ADA) and with treatment-emergent ADAs (TE ADA) to LY3478045 may be tabulated and listed if available.

For subjects who are ADA negative at baseline, TE ADAs are defined as those with a signal increase, greater than assay variability, compared to baseline. The frequency of cross-reactive binding to native GIP, GLP-1 or neutralizing antibodies may also be tabulated in TE ADA+ participants, when available.

9.6.7 Body Weight

Body weight data will be listed. In Part B, it will also be summarized by treatment group, together with changes from baseline (Day -1 [Cohorts 1 and 3], Day -3 [Cohorts 2 and 4]).

9.6.8 Hepatic Monitoring

If a subject experiences elevated alanine aminotransferase $\geq 3 \times$ upper limit of normal (ULN), alkaline phosphatase $\geq 2 \times$ ULN, or elevated total bilirubin $\geq 2 \times$ ULN, liver tests will be performed to confirm the abnormality. Additional safety data may be collected if required, as defined in the protocol. Where applicable, the following will be presented.

The subjects' liver disease history and associated person liver disease history data will be listed. Any concomitant medications that have potential for hepatotoxicity, including acetaminophen will be listed. Results from any hepatic monitoring procedures, such as a magnetic resonance elastography scan, and biopsy assessments will be listed, if performed.

Hepatic risk factor assessment data will be listed. Liver related signs and symptoms data will be summarized by Part and treatment, and listed. Alcohol and recreational drug use data will also be listed.

All hepatic chemistry, hematology, coagulation, and serology data will be listed. Values outside the reference ranges will be flagged on the individual subject data listings.

9.6.9 Testicular Safety assessment

Observations of total testosterone, follicle-stimulating hormone, and luteinizing hormone will be listed. Values outside the reference range will be flagged in Cohorts 1 and 2 for Part B on the individual subject data listings.

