9.4.5.2. Testicular safety

Male subjects will be enrolled in this trial only if they agree to comply with the contraception requirements specified in this protocol.

In Part B (MAD), blood samples for evaluating hormonal biomarkers of testicular injury (serum concentrations of total testosterone, follicle-stimulating hormone, and luteinizing hormone) will be collected at the visits and times specified in the Schedule of Activities (Section 2).

To mitigate risks of testicular injury, in Part B of the study (MAD), male participants' dose will be restricted to the dose with predicted mean exposure not exceeding **CCI** **CCI** which is the lowest dose tested in dogs with no testicular findings.

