10.3.1.2. Statistical Evaluation of Safety

Safety parameters that will be assessed include clinical laboratory parameters, vital signs, and ECG parameters. All laboratory values will be reported in both absolute values and changes from baseline in units acceptable to the FDA. The parameters will be listed and summarized using standard descriptive statistics.

Analyses may be performed to determine the effects of PK parameters on QT interval corrected. A concentration-response analysis will be performed according to International Council for Harmonisation (ICH)-E14 (the clinical evaluation of QT/QTc interval prolongation and proarrhythmic potential for non-antiarrhythmic drugs) guidelines.

Additional analysis will be performed if warranted upon review of the data.

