9.6.3 Clinical laboratory parameters

All clinical chemistry and hematology data will be summarized by parameter and treatment group together with changes from baseline, where baseline is defined as the Day 1 predose assessment, and listed. Urinalysis data will be listed. Additionally, clinical chemistry, hematology and urinalysis data outside the reference ranges will be listed and flagged on individual subject data listings.

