11. CHANGES FROM THE PROTOCOL SPECIFIED STATISTICAL ANALYSES

There were no changes from the protocol specified statistical analyses.

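### The SAP lists and flags the hormonal biomarkers of testicular injury but does not summarize their change from baseline, which the protocol appears to require, and it declares no departure.

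*SAP*

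**What the plan says.** Protocol 9.4.5.2 provides that in Part B "blood samples for evaluating hormonal biomarkers of testicular injury (serum concentrations of total testosterone, follicle-stimulating hormone, and luteinizing hormone) will be collected", at the times in the Schedule of Activities. The same section restricts male exposure in Part B because of testicular findings in dogs.

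On analysis, Protocol 10.3.1.2 says "All laboratory values will be reported in both absolute values and changes from baseline in units acceptable to the FDA" and then "The parameters will be listed and summarized using standard descriptive statistics".

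SAP 9.6.9 has two sentences on the panel: "Observations of total testosterone, follicle-stimulating hormone, and luteinizing hormone will be listed" and "Values outside the reference range will be flagged in Cohorts 1 and 2 for Part B on the individual subject data listings". It mentions no summary, treatment grouping or change from baseline. SAP 9.6.3, by contrast, says "All clinical chemistry and hematology data will be summarized by parameter and treatment group together with changes from baseline", with Day 1 predose as baseline.

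Three other SAP statements bear on this. Section 9.1 limits summary statistics and analyses to data for which the SAP sets them out. Section 3 says the SAP supersedes the protocol's statistical considerations but will identify substantial differences. Section 11 then states "There were no changes from the protocol specified statistical analyses".

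**The concern.** Safety is the primary objective, and clinically significant changes in safety laboratory parameters form part of the primary endpoint (Protocol Section 4). The testis is an organ for which the protocol sets both a sex-specific exposure limit and a dedicated blood panel. Yet that panel gets less analysis than routine chemistry and hematology (SAP 9.6.3) or Part B body weight (SAP 9.6.7), all of which are summarized with changes from baseline.

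An out-of-range flag compares a man with a population. It does not compare him with himself, or treated men with placebo. A parallel fall in testosterone, or a parallel rise in FSH or LH, can leave most men inside the range. The Day 1 and Day 2 samples are matched for time of day, which suits a within-subject comparison, but the SAP does not make one.

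**Working it through.** The documents give no figure to reproduce on this point. The main check sets the rules side by side.

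| Question | Protocol | SAP |
|---|---|---|
| Are the values listed? | Yes (10.3.1.2) | Yes (9.6.9) |
| Is change from baseline reported? | Yes, for all laboratory values (10.3.1.2) | Not for the hormones (9.6.9); yes for chemistry and hematology (9.6.3) |
| Is there a descriptive summary? | Yes (10.3.1.2) | Not for the hormones; 9.1 excludes summaries that the SAP does not detail |
| Is the departure declared? | – | Section 3 says substantial differences will be identified; Section 11 declares none |

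**Is there a baseline?** Yes. Protocol 2.2 and 2.3 show a screening sample, predose samples on Days 1 and 2, and samples at follow-up and early discontinuation. Appendix 5 counts 4 hormone samples of 3.5 mL, and 4 × 3.5 = 14 mL, its stated total. That fits screening, Day 1, Day 2 and one of follow-up or early discontinuation. The schedule tables are broken in the text available, so this reading is probable rather than certain. If it is right, the one routine on-treatment value follows a single dose, and the Day 28 value comes 14 days after the last dose on Day 14.

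**How many men?** Each Part B cohort has 6 active and 2 placebo subjects. Cohorts 1 and 2 together give at most 2 × 6 = 12 treated and 2 × 2 = 4 placebo men, and fewer if women enroll, which every Part B cohort allows.

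**How much would flags show?** This is an illustration on assumptions that the documents do not supply. The reference range is mean ± 1.96 SD, the men come from that distribution, and every treated man falls by d SD.

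- Chance of a low flag per man: p = Φ(−1.96 + d)
- Expected low flags among n men: n × p
- Chance of no low flag: (1 − p)^n

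| Fall d | p | Expected flags, n = 12 | P(no flag), n = 12 | Expected flags, n = 6 | P(no flag), n = 6 |
|---|---|---|---|---|---|
| 0.25 SD | 0.044 | 0.52 | 0.585 | 0.26 | 0.765 |
| 0.5 SD | 0.072 | 0.87 | 0.407 | 0.43 | 0.638 |
| 1 SD | 0.169 | 2.02 | 0.109 | 1.01 | 0.330 |

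For d = 0.5, p = Φ(−1.46) = 0.072, 12 × 0.072 = 0.87, and (1 − 0.072)^12 = 0.41. So 93% of men stay above the lower limit after a 0.5 SD fall, and 83% after a 1 SD fall. The same formula applies at the upper limit for a rise in FSH or LH.

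**The case against.** **The values are still reported.** A reader might infer that a within-range shift would appear nowhere in the report. The documents do not support that: SAP 9.6.9 lists every value, including Day 1 predose, and with at most 6 treated subjects per cohort an attentive reader could see a parallel fall. This stands. What is missing is a summary.

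**Further analysis is not barred.** A reader might take SAP 9.6.10, which leaves undetailed safety assessments unsummarized, as closing the matter. It does not apply, because 9.6.9 details the hormones. SAP Section 3 permits added analyses, and Protocol 10.3.1.2 foresees more if the data warrant it. This also stands, but such an analysis would be chosen after seeing the data.

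**A large fall would probably raise flags.** A reader might infer that the panel would look negative whatever happened. Assume a uniform 30% fall, log-normal values and a ratio R of upper to lower limit of 2.5 to 4. Then SD(log) = ln(R)/3.92 and p = Φ(−1.96 − ln(0.7)/SD), which gives 33% to 17% per man. Among 12 men the chance of at least one low flag is 1 − (1 − p)^12, or 99% to 89%. With no effect it is 1 − 0.975^12 = 26%. The weakness of flags therefore concerns moderate shifts and small numbers of men.

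**The protocol sentence may not cover this panel.** Protocol 10.3.1.2 introduces clinical laboratory parameters, and Appendix 2 omits testosterone and LH. That reading is arguable. But the sentence speaks of all laboratory values, and Appendix 2 includes FSH in males expressly for testicular assessment. Even on the narrow reading it is unclear whether FSH follows SAP 9.6.3 or 9.6.9.

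**Sampling limits the gain.** A table cannot describe dosing days on which no sample was taken. This is right, and it reduces the benefit. It does not justify leaving the Day 2 and follow-up changes unsummarized.

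**Conclusion.** The point holds as a mismatch between the two documents. The protocol, on its natural reading, calls for absolute values, changes from baseline and a descriptive summary. The SAP gives this panel listings and flags, and declares no change. The consequence is limited: a shift that stays within range would be neither summarized nor flagged, and would be found only by reading individual listings.

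The text supports nothing stronger. It does not show that the data would be withheld, that later analysis is excluded, or that a large effect would be missed. A formal comparison with placebo is not supported either, because the number of men is small and not fixed.

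The conclusion rests on reading the hormones as laboratory values under Protocol 10.3.1.2. The statement about time points rests on the schedule tables as far as they can be read. The flag probabilities are illustrative and depend on the assumed reference range and a uniform shift. The restriction of flags to Cohorts 1 and 2 is a separate matter.

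**What to change.** Keep the listing and flag sentences in SAP 9.6.9 and add text along these lines:

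*For male subjects in Part B, total testosterone, FSH and LH will be summarized descriptively by treatment (placebo pooled across cohorts) and scheduled time point, as absolute values and as change (or ratio) from the Day 1 predose value. Values for female subjects will be listed separately. The scheduled post-baseline samples are Day 2 and follow-up or early discontinuation, so the summary does not describe the end of the 14-day dosing period. It is descriptive because the number of men is small and not fixed.*

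Confirm the time points against the Schedule of Activities before finalizing the wording. Pooling has to be stated because SAP Section 6 lists placebo with and without the additional single-dose drug as separate treatments. If the sponsor prefers listings only, SAP Section 11 should declare the departure and give the reason.

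The cost is one extra table from data already collected. No sample, dose, eligibility rule or clinical procedure changes.

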9.6.10 Other assessments

All other safety assessments not detailed in this section will be listed but not summarized or statistically analyzed.

10. INTERIM ANALYSES

No interim analyses are planned for this study except the interim access to safety, tolerability, and other PK/PD data to guide dose selection for the next dosing.

If an unplanned interim analysis is deemed necessary, the Lilly clinical pharmacologist, clinical research physician/investigator, or designee will consult with the appropriate medical director or designee to determine if it is necessary to amend the protocol.

11. CHANGES FROM THE PROTOCOL SPECIFIED STATISTICAL ANALYSES

There were no changes from the protocol specified statistical analyses.

13. DATA PRESENTATION

13.1 Derived Parameters

Individual derived parameters (e.g. PK parameters) and appropriate summary statistics will be reported to three significant figures. Observed concentration data, e.g. C_{max} should be reported as received. Observed time data, e.g. t_{max} should be reported as received. N and percentage values

should be reported as whole numbers. Median values should be treated as an observed parameter and reported to the same number of decimal places as minimum and maximum values.

13.2 Missing Data

Missing data will not be displayed in listings.

